4.2.2 Protocol Specific Requirements For 10107 Site Registration

Upon site registration approval in RSS, the enrolling site may access OPEN to complete enrollments. The enrolling site will select their credentialed provider treating the subject in the OPEN credentialing screen, and may need to answer additional questions related to treatment in the eligibility checklist.

- A site initiation teleconference (SIV TC) with the lead site

4.2.3 Requirements For Protocol # 10107 Site Registration for Sites Participating in the Medidata Patient Cloud ePRO to collect PRO-CTCAE Items

- After the patient is registered to the trial via OPEN, and if the patient reads or understands English, and is willing to participate in electronic data collection using their personal smart phone or tablet (or clinic owned tablets if available), the site staff will then need to complete a separate registration for the patient to

the Patient Cloud ePRO through iMedidata.

- For sites participating in the ePRO pilot, site CRAs must complete training prior to registering to ePRO. This training includes an eLearning module that will be made available in each CRA's iMedidata screen (Tasks panel) titled "Patient Cloud: Registering Your Subjects", as well as review of ePRO resource materials available on the CTSU website. Training information is in Appendix D.
- For patients who agree to participate, the pre-study visit questionnaires will not be available in paper form. Therefore, site CRAs must take the ePRO training when a patient is identified for the study, if they have not already taken the training so they can perform the ePRO registration.
- The registration to the Patient Cloud ePRO will create a unique patient registration code that the site staff will provide to the patient. The patient (with assistance from the site staff) should be instructed to download the Patient Cloud ePRO app onto his/her own device (IOS, Android, phone or tablet) and use the unique patient registration code to create an account. Once the patient's account is set up, the patient will be able to complete the submission of patient reported outcomes electronically for the trial.
- For sites providing a shared institutional device for use by multiple patients on site, the site staff should assist the patient with access and registration to the Patient Cloud ePRO app and the patient can then complete the electronic data submission independently. Site staff may need to assist patients with logging onto the device at each visit.

4.2.4 Submitting Regulatory Documents

Submit required forms and documents to the CTSU Regulatory Office via the Regulatory Submission Portal on the CTSU website.

To access the Regulatory Submission Portal, log on to the CTSU members' website → Regulatory → Regulatory Submission.

Institutions with patients waiting that are unable to use the Regulatory Submission Portal should alert the CTSU Regulatory Office immediately at [name] in order to receive further instruction and support.

4.2.5 Checking Site Registration Status

You can verify your site's registration status on the members' side of the CTSU website.

- Log on to the CTSU members' website
- Click on *Regulatory* at the top of your screen

- Click on *Site Registration*
- Enter your 5-character CTEP Institution Code and click on Go

Note: The status shown only reflects institutional compliance with site registration requirements as outlined above. It does not reflect compliance with protocol requirements for individuals participating on the protocol or the enrolling investigator's status with the NCI or their affiliated networks.

4.3 Patient Registration

4.3.1 OPEN / IWRS

The Oncology Patient Enrollment Network (OPEN) is a web-based registration system available on a 24/7 basis. OPEN is integrated with CTSU regulatory and roster data and with the Lead Protocol Organization (LPOs) registration/randomization systems or Theradex Interactive Web Response System (IWRS) for retrieval of patient registration/randomization assignment. OPEN will populate the patient enrollment data in NCI's clinical data management system, Medidata Rave.

Requirements for OPEN access:

- A valid CTEP-IAM account.
- To perform enrollments or request slot reservations: Be on an LPO roster, ETCTN Corresponding roster, or Participating Organization roster with the role of Registrar. Registrars must hold a minimum of an AP registration type.
- If a DTL is required for the study, the registrar(s) must hold the OPEN Registrar task on the DTL for the site.
- Have an approved site registration for a protocol prior to patient enrollment.

To assign an Investigator (IVR) or Non-Physician Investigator (NPIVR) as the treating, crediting, consenting, drug shipment (IVR only), or receiving investigator for a patient transfer in OPEN, the IVR or NPIVR must list the IRB number used on the site's IRB approval on their Form FDA 1572 in RCR. If a DTL is required for the study, the IVR or NPIVR must be assigned the appropriate OPEN-related tasks on the DTL.

Prior to accessing OPEN, site staff should verify the following:

- Patient has met all eligibility criteria within the protocol stated timeframes, and
- All patients have signed an appropriate consent form and HIPAA authorization form (if applicable).

Note: The OPEN system will provide the site with a printable confirmation of registration and treatment information. Please print this confirmation for your records.

Access OPEN at <https://open.ctsu.org> or from the OPEN link on the CTSU members' website. Further instructional information is in the OPEN section of the CTSU website at

<https://www.ctsu.org> or <https://open.ctsu.org>. For any additional questions, contact the CTSU Help Desk at [name] or [contact].

Patient enrollment for this study will be facilitated using the Slot Reservation System in conjunction with the registration system in OPEN. Prior to discussing protocol entry with the patient, all site staff must use the CTSU OPEN Slot Reservation System to ensure that a slot on the protocol is available to the patient. Once a slot reservation confirmation is obtained, site staff may then proceed to enroll the patient to this study.

4.3.1 OPEN/IWRS Questions?

Further instructional information on OPEN is provided on the OPEN tab of the CTSU website at <https://www.ctsu.org> or at <https://open.ctsu.org>. For any additional questions contact the CTSU Help Desk at [name] or [contact].

Theradex has developed a Slot Reservations and Cohort Management User Guide, which is available on the Theradex website: <http://www.theradex.com/clinicalTechnologies/?National-Cancer-Institute-NCI-11>. This link to the Theradex website is also on the CTSU website OPEN tab. For questions about the use of IWRS for slot reservations, contact the Theradex Helpdesk at [contact] or Theradex main number [contact]; [contact].

4.4 General Guidelines

Following registration, patients should begin protocol treatment within 14 days. Issues that would cause treatment delays should be discussed with the Principal Investigator. If a patient does not receive protocol therapy following registration, the patient's registration on the study may be canceled. The Study Coordinator should be notified of cancellations as soon as possible.

5. TREATMENT PLAN

5.1 Agent Administration

Treatment will be administered on an outpatient basis. Reported adverse events and potential risks are described in Section 7. Appropriate dose modifications are described in Section 6. No investigational or commercial agents or therapies other than those described below may be administered with the intent to treat the patient's malignancy.

Phase 2, Group 1: Pembrolizumab Alone

MK-3475 (Pembrolizumab) will be administered as a dose of 200 mg using a 30-minute IV infusion. Infusion timing should be as close to 30 minutes as possible; however, a window of minus 5 minutes and plus 10 minutes is permitted (i.e., infusion time is 30 minutes: minus 5 minutes to plus 10 minutes). Treatment with pembrolizumab may continue for up to 24 months total. Refer to Section 5.1.2.

Phase 1 and Phase 2, Group 2: Anetumab ravidansine and Pembrolizumab

Pembrolizumab will be administered as described for Group 1; anetumab ravidansine will be administered at 6.5 mg/kg as determined by the phase 1 safety lead-in portion of the study using

a 60-minute IV infusion. Infusion timing should be as close to 60 minutes as possible; however, a window of minus 5 minutes and plus 10 minutes is permitted (i.e., infusion time is 60 minutes: minus 5 minutes to plus 10 minutes). The study drugs are administered in the following order when given together: anetumab raptansine first followed by pembrolizumab. Treatment with anetumab raptansine may continue for up to 12 months total. Treatment with pembrolizumab may continue for up to 24 months total. For patients receiving both drugs, the intravenous catheter must be flushed with either D5W or 0.9% sodium chloride between the two infusions. Pre-medication is not needed unless a patient develops an infusion reaction. Refer to sections 5.1.1 and 5.1.2.

Phase 1 Dose Safety Run-In Schedule

Dose De-Escalation Schedule for Phase 1 Study ^{1,2}		
Dose Level	Dose	
	Anetumab ravidansine (mg/kg)	Pembrolizumab (mg)
1*	6.5	200
-1	5.5	200
-2	4.5	200

1. Both agents will be given every 21 days. Anetumab ravidansine will be administered prior to pembrolizumab.
 2. In obese patients, anetumab ravidansine dose should be calculated considering a maximum weight of 100 kg

* Starting dose level

Randomized Phase 2 Dose Schedule

Dose Schedule for Randomized Phase 2 Study					
Agent	Premedication; Precautions	Dose	Route	Schedule	Cycle Length
Anetumab ravidansine	None	6.5 mg/kg ^{1,2}	IV over 1 hour	Days 1	21 days (3 weeks)
Pembrolizumab ³	None	200 mg ¹	IV over 30 minutes after anetumab ravidansine in patients assigned to the combination	Day 1	
1. Doses may be modified or held as per Section 6 Dosing Delays/Dose Modifications 2. In obese patients, anetumab ravidansine dose should be calculated considering a maximum weight of 100 kg 3. In subjects randomized to receive the combination, anetumab ravidansine will be administered prior to pembrolizumab when given together.					

5.1.1 Anetumab Ravtansine

Administer anetumab ravtansine as an IV infusion over 1 hour. Please refer to section 8.1.1 for compatible infusion set materials including the in-line filter.

No specific prophylactic medications are recommended for anetumab ravtansine. Full supportive care is recommended as per community standards of medical care as determined by the treating physician; however, patients should not take any medications or substances that are strong inhibitors or inducers of CYP3A4 including herbal preparation containing CYP3A4 inducers (e.g. St. John's Wort), grapefruit and grapefruit juice (CYP3A4 inhibitor) within 2 weeks before the start of study treatment or while on treatment because DM4 is a substrate of CYP3A4. Because the lists of these agents are constantly changing, it is important to regularly consult a frequently-updated medical reference for a list of drugs to avoid or minimize use of.

If a patient experiences a CTCAE Grade ≥ 2 anetumab ravtansine infusion reaction or other CTCAE Grade ≥ 2 hypersensitivity event deemed at least possibly related to anetumab ravtansine, the infusion of anetumab ravtansine will be interrupted. If treatment interruption is caused by a CTCAE Grade ≥ 2 anetumab ravtansine infusion reaction or other CTCAE Grade ≥ 2 hypersensitivity event deemed at least possibly related to anetumab ravtansine, treatment may be re-started at the time determined at the investigator's discretion. Re-treatment should be at the infusion rate reduced by 50%, along with anti-allergic prophylaxis (e.g. anti-histamines, acetaminophen, and/or corticosteroids) chosen at the investigator's discretion or according to the institutional guidelines.

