5.1.2 Pembrolizumab (MK-3475)

Pembrolizumab will be administered on Day 1 of each 3-week treatment cycle after all procedures/assessments have been completed. Pembrolizumab may be administered up to 3 days before or after the scheduled Day 1 of each cycle due to administrative reasons (up to 5 days after randomization is permitted).

Note: Dosing interruptions are permitted in the case of medical/surgical events or logistical reasons (i.e., elective surgery, unrelated medical events, patient vacation and holidays) not related to study therapy. Patients should be placed back on study therapy within 3 weeks of the scheduled interruption. The reason for interruption should be documented in the patient's study record.

Pembrolizumab will be administered as a dose of 200 mg using a 30-minute IV infusion. Infusion timing should be as close to 30 minutes as possible; however, a window of minus 5 minutes and plus 10 minutes is permitted (i.e., infusion time is 25 to 40 minutes. Please refer to section 8.1.2 for compatible infusion set materials including the in-line filter.

Anetumab ravtansine will be given prior to pembrolizumab for the combination therapy

when given together.

No specific prophylactic medications are recommended for pembrolizumab. Full supportive care is recommended as per community standards of medical care as determined by the treating physician.

Infusion-related reactions have been reported with pembrolizumab. Infusion-related reactions may present as allergic reaction (hypersensitivity), serum sickness, infusion and infusion-like reactions, cytokine release syndrome, or anaphylaxis. Mild infusion reactions can generally be treated with interruption of the infusion and medical intervention including IV fluids, antihistamines, nonsteroidal anti-inflammatory drugs, acetaminophen, and narcotics as needed. More severe or life-threatening reactions may require vasopressors, corticosteroids, and epinephrine. If symptoms resolve within one hour of stopping drug infusion, the infusion may be restarted at 50% of the original infusion rate (e.g., from 100 mL/hr to 50 mL/hr). Otherwise dosing will be held until symptoms resolve and the subject should be premedicated for the next scheduled dose. In the case of severe or life-threatening reactions, subsequent doses of pembrolizumab should not be administered.

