5.8 Criteria to Resume Treatment Following a Drug-Related Adverse Event

For non-autoimmune or inflammatory events, patients may resume treatment with study drug when the drug-related AE(s) resolve to \leq Grade 1 or baseline value, with the following exceptions:

- Patients may resume treatment in the presence of Grade 2 fatigue.
- Patients with baseline Grade 1 AST/ALT or total bilirubin who require dose delays for reasons other than a 2-grade shift in AST/ALT or total bilirubin may resume treatment in the presence of Grade 2 AST/ALT OR total bilirubin.
- Patients with combined Grade 2 AST/ALT AND total bilirubin values meeting study parameters outlined in Section 6.1 should have treatment permanently discontinued.
- Non-drug-related toxicity including hepatic, pulmonary toxicity, diarrhea, or colitis, must have resolved to baseline before treatment is resumed.
- Drug-related endocrinopathies (not including drug-related adrenal insufficiency or hypophysitis) adequately controlled with only physiologic hormone replacement may resume treatment after replacement correction and clinically stable regimen.

If the criteria to resume treatment are met, the patient should restart treatment no sooner than the next scheduled time point per protocol. However, if the treatment is delayed past the next scheduled time point per protocol, the treatment should resume at the earliest convenient point that is within the 12 week delay period.

If treatment is delayed >12 weeks, the patient must be permanently discontinued from study therapy, except as specified in Section 5.5 (Duration of Therapy).

Note: PRO-CTCAE data should not be used for determining treatment resumption following a drug-related symptomatic adverse event.

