6.2 Dose Modifications for Anetumab Ravtansine

Dose Level	Anetumab Ravtansine Dose
1	6.5 mg/kg
-1	5.5 mg/kg
-2	4.5 mg/kg

Neutrophil count decreased ^{1, 2}	Management/Next Dose
\leq Grade 1	No change in dose
Grade 2	No change in dose
Grade 3	Hold ² until $<$ Grade 2. Resume at one dose level lower.
Grade 4	Hold ² until $<$ Grade 2. Resume at one dose level lower.
1.	Patients with febrile neutropenia should hold ^{**} until $<$ grade 2 and resume at one dose level lower.
2.	G-CSF and other hematopoietic growth factors may be used during the study in the management of acute toxicity such as febrile neutropenia when clinically indicated per ASCO Recommendations for Therapeutic Use of CSF (63) or at the discretion of the investigator; however they may not be substituted for a required dose reduction.
3.	Patients requiring a delay of $>$ 12 weeks should go off protocol therapy.

Platelet count decreased¹	Management/Next Dose
≤ Grade 1	No change in dose
Grade 2	No change in dose
Grade 3	Hold ² until < Grade 2. Resume at one dose level lower.
Grade 4	Hold ² until < Grade 2. Resume at one dose level lower.
1.	Patients with active bleeding related to drug-induced thrombocytopenia should reduce by one dose level.
2.	Patients requiring a delay of > 12 weeks should go off protocol therapy.

Non-hematologic toxicities	Management/Next Dose
≤ Grade 1	No change in dose.
Grade 2	No change in dose.
Grade 3	Hold ¹ until ≤ Grade 2. Resume at same level or at one dose level lower, per investigator's discretion. ²
Grade 4	Off protocol therapy
1.	Patients requiring a delay of > 12 weeks should go off protocol therapy.
2.	Patients requiring > two dose reductions should go off protocol therapy.

Corneal Epitheliopathy	Definition	Management/Next Dose^{1, 2}
Grade 0	No pathologic changes	No change in anetumab ravtansine; ocular lubricants at discretion of investigator or ophthalmologist
Grade 1	Any stage of superficial punctate keratitis (SPK; as per the Oxford Schema for grading SPK from stage 0 to IV)	No change in anetumab ravtansine; ocular lubricants; add topical steroids if SPK shows treatment emergent progression by ≥ 2 SPK grades

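### After a grade 4 anetumab ravtansine infusion or hypersensitivity reaction, Section 5.1.1 permits re-treatment while Section 6.2 requires a stop, and nothing says which governs

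*Combined protocol and SAP*

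**What the plan says.** Section 5.1.1 (Anetumab Ravtansine) opens its rule with "If a patient experiences a CTCAE Grade ≥ 2 anetumab ravtansine infusion reaction or other CTCAE Grade ≥ 2 hypersensitivity event" and limits it to events at least possibly related to the drug. The infusion is interrupted. The next sentence repeats the same grade range and says "treatment may be re-started at the time determined at" the investigator's discretion. The conditions follow: "Re-treatment should be at the infusion rate reduced by 50%, along with anti-allergic prophylaxis". The section sets no upper grade, names no resolution grade and does not refer to Section 6.2.

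Section 6.2 (Dose Modifications for Anetumab Ravtansine) has separate tables for neutrophils, platelets and corneal epitheliopathy, and a general table headed "Non-hematologic toxicities". In the general table a grade 3 event is held until grade 2 or lower, and a grade 4 event means the patient goes "off protocol therapy". Neither the table nor its footnotes mention infusion or hypersensitivity reactions.

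Section 5.1.2 gives pembrolizumab a severity cut-off for its own infusion reactions: "In the case of severe or life-threatening reactions, subsequent doses of pembrolizumab should not be administered". Section 5.1.1 has no counterpart for anetumab ravtansine.

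**The concern.** A grade 4 reaction during the anetumab ravtansine infusion meets the entry condition of both sections. A site that follows the rule written for this kind of reaction may re-expose the patient. A site that follows the general toxicity table must take the patient off treatment. Re-exposure after a grade 4 reaction should not depend on which section a site consults. Only patients given anetumab ravtansine are affected, which in the randomized part means Group 2, so handling of the same event could differ between sites within the experimental arm.

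**Working it through.** The plan states no figure on this point and no arithmetic decides it. The check is whether any passage removes the overlap through a grade limit, an exception or an order of precedence.

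1. **Grade range.** Section 5.1.1 applies from grade 2 upward with no ceiling. Grade 4 is not named, but the open range includes it.

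2. **Which 6.2 table applies.** An infusion or hypersensitivity reaction is not a neutrophil, platelet or corneal event. The general non-hematologic table is the only one left, and its grade 4 row has no exception.

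3. **The two instructions for one grade 4 event.**

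| | Section 5.1.1 | Section 6.2, non-hematologic |
|---|---|---|
| Grades covered | 2 and above | each grade separately |
| Grade 4 action | restart permitted, timing left to the investigator | off protocol therapy |
| Conditions | half rate, prophylaxis | none; no discretion |
| Reference to the other section | none | none |

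4. **Precedence.** Section 5.1 says "Appropriate dose modifications are described in Section 6". In its Group 2 paragraph, directly after mentioning pre-medication for a patient who develops an infusion reaction, it sends the reader to 5.1.1 and 5.1.2. Footnote 1 of the phase 2 dose table says that doses may be modified or held under Section 6, which does not settle precedence either.

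5. **DLT section.** Section 5.2.1 lists anetumab reactions not controlled by a slower rate and prophylaxis, and any treatment-related grade 4 event. It sends management of all listed events to Section 6. Section 6.2 has no row for infusion reactions, so the pointer leads back to the general table without saying that 5.1.1 yields to it.

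6. **Other candidates.** Section 5.8 says that, for the events it covers, "patients may resume treatment with study drug when the drug-related AE(s) resolve to" grade 1 or lower or baseline. This is a condition on resuming and does not exclude grade 4 reactions. Section 6.4 deals with continuing one agent when the other is held or stopped, so it does not address re-exposure to the agent that caused the reaction.

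None of these provides a ceiling, an exception or a precedence rule, so the overlap at grade 4 remains.

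**The case against.** The best defence is that the sections have different jobs. Section 5.1.1 sits under agent administration and describes how re-treatment is given. Section 6.2 decides whether and at what level the next dose is given. On that reading 5.1.1 operates only where 6.2 still allows dosing, and the pointers to Section 6 in 5.1, the dose-table footnote and 5.2.1 support it. This is a sensible reading and may be what was intended, but no passage states it. Section 5.1 also directs the reader to 5.1.1 for this very event, and a site that follows 5.1.1 as written may re-treat a patient whom 6.2 removes.

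The defence is right on three further matters, where a reader might infer more than the text supports.

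- **Opposite commands.** Section 5.1.1 permits a restart and does not order one. A site that stops a grade 4 patient breaches neither section. The defect is a permission without an upper bound set against a mandatory stop.
- **A second contradiction at grade 3.** Section 5.1.1 is silent on resolution, while 6.2 requires grade 2 or lower and 5.8, where it applies, grade 1 or lower or baseline. A site can wait for resolution and still comply with 5.1.1. Silence alongside a criterion is a gap in cross-referencing, not a conflict.
- **An expected number of patients.** Section 7.1.1 places infusion related reaction in the category of at most 20%, without splitting it by grade. It lists allergic reaction and anaphylaxis among reported events with insufficient evidence of causation. Section 2.3.2.2 reports no DLT in 12 evaluable patients at this dose, which is too few to exclude a low rate. The chance that at least one of 49 Group 2 patients is affected is 1 − (1 − p)^49. An assumed p of 0.1% gives 4.8% and an assumed p of 3% gives 77.5%, so the answer is only the assumption restated.

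**Conclusion.** The point stands for grade 4. The same reaction falls under a discretionary permission to re-treat in Section 5.1.1 and a mandatory stop in Section 6.2, and the documents do not rank them. This rests on two plain readings: that grade 2 or higher includes grade 4, and that these reactions belong in the general non-hematologic table because no other table fits.

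Its importance is patient safety and internal consistency. No frequency is claimed.

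A reader might infer that the efficacy comparison is at risk, but the documents do not support that. Section 13.1.2 counts all eligible patients who started treatment. Section 13.8.2 keeps patients in the response analysis despite an incorrect schedule or drug administration. The stopping rule in Section 13.7.3 counts patients with grade 4 or higher non-hematologic events at least possibly related to treatment, whether or not they are re-treated. Little effect on the primary analysis is expected.

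**What to change.** Reconcile 5.1.1 with 6.2 at the next amendment, in one of two ways:

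- state in 5.1.1 the grades to which the restart permission applies; or
- add an infusion/hypersensitivity row to 6.2 and make 5.1.1 defer to it.

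Either way, each grade should have one instruction. Which instruction stands is for the clinical team, and this review takes no position on it.

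In the same edit, have 5.1.1 cross-reference the resolution criteria in 6.2 and 5.8 and say which applies to these reactions, since those two sections name different resolution grades. Bring the Section 6 pointer in 5.2.1 into line, so that it leads to text that covers infusion reactions.

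The cost is a sentence or a table row plus cross-references, with no added patients, procedures or analyses.
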